At the beginning of the 2nd trimester, women will be randomized to HCL therapy or SAPT. Women who were on multiple daily injections at baseline will complete a minimum of 4 weeks of therapy in SAPT mode prior to being randomized. All women in the HCL arm will be trained on the HCL technology. For the first 2 weeks after training, women will be contacted daily for insulin adjustments (if applicable) and trouble-shooting of device wearing. Frequency of insulin adjustments will be guided by glucose levels, level of insulin resistance, and willingness to contact study staff to ask for assistance, where (in general) women with a larger-than-expected number of glucose levels above or below ADA targets, dramatic insulin resistance, and unwilling to proactively contact study staff for assistance will be contacted more frequently for pump follow-up and adjustments as necessary. For the HCL group, insulin adjustments will be changes to carbohydrate-to-insulin doses and/or active insulin time. For the SAPT group, insulin adjustments will be changes to basal rates, carbohydrate-to-insulin doses, correction factors, and/or active insulin time. The first 5 women in each arm of the study will be asked to complete 7-point profiles for 2 weeks after randomization. Women will attend research and clinic visits at the Barbara Davis Center and Ohio State University every 4 weeks for routine diabetes care in pregnancy, downloading of study devices, and outcomes measurements. CGM, glucose meter, and pump downloads will also be reviewed throughout the study to ensure compliance with treatment assignment and the study protocol. Insulin pump adjustments will be made at least once every 4 weeks at face-to-face clinic/research visits and every week in between face-to-face visits, as per routine clinical care. When recommendations for pump adjustments are made during the interim weekly remote monitoring, we will verify that participants correctly entered the new settings. Acceptable forms of verification will include, verbal or written confirmation of new pump settings by the participant, a new upload of settings in CareLink, sending screen shots or pictures of the new settings from the participant’s pump. Women will be contacted every week in between research visits to inquire about open- and closed-loop wear (HCL group) and for pump adjustments as needed (both groups) (See Table 2 and Figure 2). As per routine clinical care, we will recommend that women start low-dose aspirin therapy (81-162 mg orally daily) between 12 and 16 weeks gestations, to reduce the risk of preeclampsia, unless there is a contraindication to aspirin therapy. At the start of the 2nd and 3rd trimesters, women will be given handouts describing conditions of which they should be aware for that trimester (see appendix).

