Hemoglobin A1C will be measured every 4 weeks in pregnancy and 4-6 weeks post-partum. The A1C measurements will be those used for clinical point of care at each site. These assays are DCCT aligned for both sites. Routine blood and urine tests will be performed in all subjects in each trimester (see Table 2), and serum, plasma, and urine samples will be collected and stored at -80 degrees as a biorepository for future assays. The Hypoglycemia Fear Questionnaire, Insulin Delivery Satisfaction Survey, Glucose Monitoring Satisfaction Survey, INSPIRE Questionnaire (HCL only), and Medical Outcomes Study (MOS) Short Form-36 (SF-36) will be administered at baseline, once every trimester (6-8 weeks, 18-20 weeks, 30-32 weeks) and 4-6 weeks post-partum. We will screen for diabetes complications at baseline, once per trimester, and post-partum. Women will be administered a questionnaire inquiring about breastfeeding at their final post-partum visit. We will request records of the hospital admission at delivery to collect data about maternal and fetal outcomes. Should subjects experience emotional distress during the pregnancy or post-partum period, a licensed clinical psychologist will provide

them with resources for therapy either at the Barbara Davis Center or closer to where they live per subject preference.

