To address **Specific Aim 1**, we will compare percent of time spent in the SH range of <54 mg/dL on CGM (primary outcome) using a non-inferiority t-test with a margin of 1%. Counts of DKA and adverse skin reactions (secondary outcomes) will be compared between groups (HCL vs. SAPT) using t-tests for normally distributed variables and Wilcoxon Rank-Sum test for non-normal variables. As the purpose of this study is to demonstrate that HCL has a similar safety profile compared to SAPT during pregnancy, we will use a non-inferiority test. As a secondary analysis of events such as SH, DKA, and skin reactions, we will account for potential differential follow-up times due to miscarriage, drop-out, and withdrawal using Poisson regression with an offset for follow-up time. To address **Specific Aim 2**, we will compare CGM glucose variables (primary outcomes for glucose variables will be time spent <54, <63, 63-140, >140, >180 mg/dL; secondary outcomes will be glucose SD, J index, HBGI, LBG, MAGE, and CONGAn) and fear of hypoglycemia score between groups (HCL vs. SAPT) using t-tests for normally distributed variables and Wilcoxon Rank-Sum test for non-normally distributed variables. We will examine the buckets of time spent in each range (hypoglycemia, in range, and hyperglycemia) by day and night, as well as day-to-day variation. Mean glucose variables and hypoglycemia fear scores will be compared during each trimester of pregnancy and 4-6 weeks post-partum using mixed models. To address **Specific Aim 3**, we will compare SF-36 scores, insulin device satisfaction and glucose device satisfaction by group (HCL vs. SAPT) using t-tests if scores are normally distributed and Wilcoxon Rank-Sum test if scores are non-normal. We will analyze changes in INSPIRE Questionnaire scores over time in the HCL group. **Specific Aim 4** is an exploratory aim, and for this aim we will examine rates of fetal loss, preeclampsia, cesarean section, LGA, and neonatal hypoglycemia using Chi-square tests. We will account for potential differential follow-up times due to miscarriage, drop-out, and withdrawal using Poisson regression with an offset for follow-up time as a sensitivity analysis, in addition to the proposed chi-square tests in the exploratory analyses of fetal loss, preeclampsia, Caesarean section, LGA, and neonatal hypoglycemia. We will use mixed models to analyze changes in repeated measures, such as glycemia variables and hypoglycemia fear scores by trimester. We will evaluate the percent of time spent in closed loop by trimester as a feasibility outcome that is important to the next step of a larger clinical trial with efficacy outcomes.

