
For women who discontinue CGM therapy during the study, we will do an intention to treat analysis of above-stated outcomes. The alpha level will be 0.05 for all analyses, except the non-inferiority tests (alpha = 0.025). The use of mixed models and Poisson regression will allow for analysis of data for the portion of the study completed with CGM therapy.

**Power and Sample Size Calculations:** The primary outcome for **Specific Aim 1** is percent of time spent <54 mg/dL on CGM. With a sample size of 10 women per group (20 study completers), we will have 80% power to detect non-inferiority using a one-sided alpha of 0.025 and a non-inferiority margin of 1.5% of time spent <54 mg/dL for HCL compared to SAPT, using estimates of variability from the PI's current study of CGM use during pregnancy. The standard deviation of time spent <54 mg/dL based on data from the PI's current study of CGM use during pregnancy was 1.1%. For **Specific Aim 2**, with a sample size of 10 women per group (20 study completers), we will have 83% power to detect a difference in time spent in target glucose range (65-140 mg/dL, this range was used in the power calculations because at that time there was no consensus on optimal time in range in pregnancy) of 3.3 hours/day (13.8%) between HCL to SAPT, assuming a standard deviation of 2.5 hours/day (effect size=1.0 SD). This is similar to effect sizes reported in another artificial pancreas study showing a difference of 2.5 hours/day (10.4%) between groups and a study of HCL in pregnancy (in a crossover design) showing a difference of 3.6 hours/day (15.2%). While this study is not powered to detect significant differences in maternal-fetal outcomes as described in **Specific Aim 4**, our goal is to provide estimates and preliminary data on these outcomes to inform the sample size needed for a larger trial focused on these outcomes, once the safety of the HCL system in pregnancy has been established.

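### Aim 3 names a t-test or Wilcoxon test for questionnaires scored three times after randomization, without saying which visit or summary is tested; one mixed model per score would settle it without new data.

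*Combined protocol and SAP*

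**What the plan says.** The Aim 3 paragraph of Section IV.F (Statistical Analysis Plan) states: "we will compare SF-36 scores, insulin device satisfaction and glucose device satisfaction by group (HCL vs. SAPT) using t-tests if scores are normally distributed", and a Wilcoxon rank-sum test if they are not. No visit, average, change score or baseline adjustment is given. The only other Aim 3 analysis concerns one arm: "We will analyze changes in INSPIRE Questionnaire scores over time in the HCL group".

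Section IV.C (Study Design and Research Methods) says that the questionnaires "will be administered at baseline, once every trimester (6-8 weeks, 18-20 weeks, 30-32 weeks) and 4-6 weeks post-partum". It places randomization at the start of the 2nd "trimester, women will be randomized to HCL therapy or SAPT". Three scheduled scores therefore follow randomization in each arm, and the enrolment and first-trimester scores precede it.

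Mixed models appear twice in Section IV.F. Under Aim 2: "Mean glucose variables and hypoglycemia fear scores will be compared during each trimester of pregnancy and 4-6 weeks post-partum using mixed models". After Aim 4, as a general statement: "We will use mixed models to analyze changes in repeated measures, such as glycemia variables and hypoglycemia fear scores by trimester". On error rates, the section says: "The alpha level will be 0.05 for all analyses, except the non-inferiority tests (alpha = 0.025". No multiplicity adjustment is described.

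**The concern.** Section II frames Aim 3 over the second and third trimesters and the early post-partum period together, so the question covers all three post-randomization scores. An independent-samples test needs one number per woman, and the plan does not say which number.

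Two literal readings cause trouble. If one visit is tested, the other scores are unused and a woman who misses that visit drops out of the comparison. If every visit is tested at 0.05, one hypothesis gets three answers and a raised false-positive rate. Because the choice is open, it could also be made after the scores are seen.

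About 10 women per arm are expected to complete. Hypothesis SA 3.2 (HCL more acceptable) therefore has limited power at any one visit. Section IV.C expects losses to miscarriage, drop-out and loss to follow-up, so incomplete series are likely.

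**Working it through.** **Closest stated figure.** The plan gives no power, effect size or SD for Aim 3. The nearest is Aim 2: "with a sample size of 10 women per group (20 study completers), we will have 83% power to detect a difference" of 3.3 hours/day with SD 2.5.
- SE = 2.5 × √(2/10) = 1.118, and 3.3/1.118 = 2.952.
- Normal approximation: Φ(2.952 − 1.960) = 83.9%, which reproduces the stated 83%. The exact noncentral t gives 79.7%.
- The ratio 3.3/2.5 is 1.32 SD, not the 1.0 SD printed beside it. At 1.0 SD, power with 10 per arm is 60.9% (normal) or 56.2% (t).

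**Inputs for Aim 3.** From the plan: 10 per arm, alpha 0.05 (taken as two-sided) and three post-randomization scores. Assumed, because the documents do not give them: within-woman correlation r = 0.5 to 0.8, equal SDs, complete data and the same effect at every visit.

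**One visit against the average of three.** The variance of the mean of three equally correlated scores is SD²(1 + 2r)/3.

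| | One visit | Three, r = 0.5 | Three, r = 0.8 |
|---|---|---|---|
| Relative SE, √((1+2r)/3) | 1.00 | 0.82 | 0.93 |
| Power at 1.0 SD (noncentral t) | 56% | 74% | 62% |
| Difference detectable with 80% power | 1.32 SD | 1.08 SD | 1.23 SD |

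The SE falls by about 18% at r = 0.5 and 7% at r = 0.8.

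**Testing each visit at 0.05.** With independent tests, 1 − 0.95³ = 14.3%. Simulating three correlated t-tests with 10 per arm and no true effect gives 12.5% at r = 0.5 and 10.2% at r = 0.8, per scale.

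**Adding the pre-randomization score.** If it has the same r with each later score, the relative SE of the three-visit average is √((1+2r)/3 − r²):
- r = 0.5: √(0.667 − 0.250) = 0.65.
- r = 0.8: √(0.867 − 0.640) = 0.48.
- A baseline-adjusted single visit, √(1 − r²), gives 0.87 and 0.60.

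Equal r may be optimistic for IDSS, since women enter on injections or on their own pump and so rate a different device at baseline.

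**If the effect is not constant.** Suppose it is 1.0 SD at both pregnancy visits and 0.5 SD post-partum. The average is (1 + 1 + 0.5)/3 = 0.83 SD, and three-visit power without baseline is 58% (r = 0.5) or 47% (r = 0.8), against 56% at one pregnancy visit. Averaging only the two pregnancy visits gives relative SE √((1+r)/2) = 0.87 or 0.95, and power 69% or 61%.

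**The case against.** A reader might infer that the plan rules out mixed models for Aim 3 and must therefore either throw away two of the three scores or triple the tests. The documents do not support that, for two reasons.

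First, the general mixed-model sentence offers glycemia variables and fear scores as examples, not as a closed list. SF-36, IDSS and GMSS are repeated measures on the same schedule as the fear survey. Aim 2 also pairs t-tests with mixed models, so a t-test in the Aim 3 sentence does not exclude a model. This stands, and the fair description is ambiguity. It does not close the gap: Aim 2 gets its own mixed-model sentence and Aim 3 does not, and on any reading no deciding contrast is named.

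Second, a t-test on each woman's mean post-randomization score would use all three visits in one test. With complete data it gives the same arm difference as an equal-weight model contrast. This also stands, but the plan does not specify that test either. With incomplete series, such means would cover different visits in different women. Section IV.F itself gives the use of partial data as a reason for mixed models.

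The constant-effect assumption can fairly be challenged. Section IV.C has HCL women in manual mode for labor and delivery, with auto mode resumed post-partum at the investigator's discretion. The calculation above shows that a weaker post-partum effect can remove the gain in power. Finally, Aim 3 is secondary in a pilot that claims no power for it, which limits the importance of the point.

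**Conclusion.** The concern holds as an unresolved choice of analysis for which a better method is available at almost no cost. The plan names a two-sample test for scores measured three times after randomization, does not say what is tested, and leaves unclear whether its mixed-model provision applies.

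The size depends on the comparator:
- Against a single-visit test, averaging lowers the SE by about 7-18%, on the assumptions listed in the working.
- Against visit-wise testing, a single contrast brings the false-positive chance per scale from about 10-12.5% back to 5%.
- Against a t-test on each woman's mean score, averaging gains nothing. What remains is baseline adjustment and the handling of incomplete series.

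The 36% drop-out allowance in Section IV.C includes screen failures, so it does not show how many questionnaires will be missing. The power argument bears on SA 3.2. SA 3.1 expects similar quality of life, which a non-significant difference cannot establish under any of these methods.

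**What to change.** In the Aim 3 paragraph of Section IV.F:

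- Analyse SF-36, IDSS and GMSS with one mixed model per score on all post-randomization visits. Include arm, visit, arm-by-visit and the pre-randomization score (say which one; the last before randomization is natural). Use a small-sample degrees-of-freedom correction such as Kenward-Roger.
- Pre-specify one contrast per score: the arm difference averaged over the three post-randomization visits, which matches the span of Aim 3.
- Report visit-specific differences, including post-partum, descriptively with confidence intervals, so that a changing effect can be seen.
- If scores are clearly non-normal, keep a rank-based test on each woman's mean post-randomization score as a sensitivity analysis.
- For SA 3.1, report the confidence interval and state that a non-significant result will not be read as similarity.
- State that the model uses incomplete series under a missing-at-random assumption.

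One test per score does not control error across scores. With two scales correlated 0.5 (assumed), the chance of at least one false positive is still about 9%, so the results should be labelled as secondary and unadjusted.

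The cost is SAP wording. No new data or visits are needed, and the method is already planned for the fear scores.

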**Hypothesis SA 3.1:** We hypothesize that pregnant women with T1D randomized to HCL therapy or SAPT will report similar quality of life (general mental health and general health perceptions), as measured by the Medical Outcomes Study (MOS) Short-Form 36 (SF-36), without a significant difference between groups.

**Hypothesis SA 3.2:** We hypothesize that HCL will be more acceptable to subjects than SAPT, as measured by Insulin Delivery Satisfaction Survey and the Glucose Monitoring Satisfaction Survey.

**Hypothesis SA 3.3:** We hypothesize that HCL in mid-pregnancy, late pregnancy, and post-partum will be more acceptable to subjects than SAPT in the first trimester in the same women using both modes of therapy, as measured by the INSPIRE Questionnaire.

**Specific Aim 4 (Exploratory Aim):** Evaluate maternal and fetal outcomes in pregnant women with T1D using HCL therapy compared to those using SAPT throughout gestation and in the early post-partum period.

**Hypothesis SA 4.1:** We hypothesize that rates of fetal loss, preeclampsia, cesarean section, and neonatal hypoglycemia will be similar between groups.

**Hypothesis SA 4.2:** We hypothesize that rates of large-for-gestational age infants and macrosomia (birth weight >4,000 grams) will be similar between groups.

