###### **Secondary Outcomes:**

- 3) Safety of HCL therapy compared to SAPT in women with T1D throughout gestation and the early post-partum period assessed through episodes of diabetic ketoacidosis and skin reactions.
- 4) Indices of glucose control and fear of hypoglycemia in pregnant women with T1D using HCL or SAPT therapy throughout pregnancy and early post-partum. Secondary outcomes of indices of glucose control are mean glucose  $\pm$  standard deviation, J index, High Blood Glucose Index (HBGI), Low Blood Glucose Index (LBGI), duration of hypoglycemic episodes, Mean Amplitude of Glycemic Excursions (MAGE), and Continuous Overall Net Glycemic Action (CONGAn).
- 5) Quality of life and device acceptability in women with T1D throughout gestation and the early post-partum period as measured by scores from the MOS Short-Form 36 (quality of life) and Insulin Delivery Satisfaction Survey, Glucose Monitoring Satisfaction Survey, and INSPIRE (HCL only) questionnaires (device acceptability).
- 6) Maternal and fetal outcomes in pregnant women with T1D using HCL therapy compared to those using SAPT throughout gestation and in the early post-partum period. Maternal outcomes include preeclampsia/eclampsia, cesarean delivery, and gestational weight gain. Fetal outcomes include fetal loss (miscarriage or stillbirth), large-for-gestational age, and neonatal hypoglycemia.

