Data Collection and Analyses: All glycemic data will be collected at each study visit. All other data will be collected at enrollment, 1st trimester (6-8 weeks gestation), 2nd trimester (18-20 weeks gestation), 3rd trimester (30-32 weeks gestation), and post-partum (4-6 weeks after delivery) except where otherwise indicated. Subjects enrolled between 8 weeks 1 day gestation and 11 weeks gestation who continue in the study after the run-in phase, will be allowed to complete the 1st trimester study assessments at the completion

of the run-in phase (outside the 6-8 week gestational time point). Each category of data and the pertinent specific aim (SA) to which it applies are outlined below.

(1) Screening (enrollment only): We will screen subjects with a history, physical exam, and urine or blood pregnancy test. Gestational age will be calculated based on the last menstrual period (or by viewing records of a uterine ultrasound). Subjects meeting inclusion/exclusion criteria will be invited to participate in the run-in phase. In our experience most women present to their diabetes provider for care during pregnancy prior to getting an ultrasound with an obstetrician. Eight to 11 weeks is the time frame when ultrasound dating is most accurate, but in our previous study 76.7% (33/43) of women presented prior to 8 weeks gestation. Thus, the LMP will be used for determining initial eligibility based on inclusion/exclusion criteria. Once an ultrasound is obtained, it will be used to determine the final gestational ages for each study visit.

(2) Run-in Phase: Subjects will wear the Medtronic Guardian CGM sensor continuously for 7 consecutive days. Subjects will calibrate per device instructions. Subjects will record self-monitoring blood glucose (SMBG) measurements (before meals, 2 hours after meals, and at bedtime), insulin doses, carbohydrate intake, and exercise on standardized log sheets. Subjects will be asked to download devices (glucose meter, insulin pump, and CGM) once during the run-in phase. The research staff will contact each subject after 2 days to ensure that they have access to communication methods in between research visits. Subjects will fill out a questionnaire about adverse reactions to device adhesives and wearing, as well as willingness to proceed further in the study.

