- (c) Device acceptability: We will measure HCL and SAPT device acceptability with the Insulin Delivery Satisfaction Survey (IDSS) and the Glucose Monitoring Satisfaction Survey (GMSS) in both the SAPT and HCL arms of the PICLS Study. The IDSS provides a 14-item questionnaire for people with T1D to assess patient attitudes and perspectives about insulin-related devices. The IDSS provides a total score, as well as subscales related to devices being effective, burdensome, and inconvenient. The GMSS asks 15 questions about glucose monitoring device satisfaction and provides a total score and subscales related to device openness, emotional burden, behavioral burden, and trust. We will measure HCL device acceptability with the INSPIRE Questionnaire. The INSPIRE Questionnaire provides a 22-item questionnaire for people with diabetes to assess patient thoughts and feelings specifically about how automated insulin delivery systems, such as HCL therapy, affect their worries/concerns, burdens, and management of diabetes.

(6) Maternal and Fetal Outcomes (SA 4): We will administer a survey we previously developed for the CGM pregnancy study in the preliminary data section. It inquires about breastfeeding. We will obtain records of the hospital admission at delivery for mother and baby to collect data about the labor and delivery process, maternal and fetal complications before and after delivery, baby's anthropometrics at birth (weight and length), and baby's age at delivery.

Data will be entered into REDCap (Research Electronic Data Capture). REDCap is an internal secure, computerized database system at the University of Colorado Denver. This system allows data entry, questionnaire building, data exportation to statistical packages, and is HIPAA compliant.

Data and Safety Monitoring Plan:

A Data Safety Monitoring Board (DSMB) with providers not connected with the study will oversee safety data throughout the study by convening once each quarter to review adverse events and severe adverse events. If after the first 6 months, the DSMB notes no increased harm from study participation then ongoing meetings will convene once every 6 months thereafter. It will also review stopping rules based on the number of SH events and other criteria as below (Table 5), either for an individual or for the total study group, and provide recommendations about study continuation.

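### Exploratory Aim 4 analyses fetal size only as LGA yes/no, although birth weight and age at delivery are collected; a supplementary continuous estimate would make better use of about 10 babies per arm

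*Combined protocol and SAP*

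**What the plan says.** Hypothesis SA 4.2 is worded as a statement about rates: "rates of large-for-gestational age infants and macrosomia (birth weight >4,000 grams) will be similar between groups". The Secondary Outcomes list names one measure of fetal size: "Fetal outcomes include fetal loss (miscarriage or stillbirth), large-for-gestational age, and neonatal hypoglycemia".

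The Statistical Analysis Plan calls Aim 4 exploratory and says that "for this aim we will examine rates of fetal loss, preeclampsia, cesarean section, LGA, and neonatal hypoglycemia using Chi-square tests". It adds "Poisson regression with an offset for follow-up time as a sensitivity analysis", applied to the same events, so LGA stays yes/no there too. Macrosomia, the other half of SA 4.2, is not named in the analysis of Aim 4. No analysis of birth weight on its own scale is planned.

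The data for one are due to be collected. Item (6) of Data Collection and Analyses takes from the delivery records the "baby's anthropometrics at birth (weight and length), and baby's age at delivery". Item (1) says of the dating ultrasound that "it will be used to determine the final gestational ages for each study visit".

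On purpose, the Power and Sample Size paragraph says the study is not powered for maternal-fetal outcomes and that "our goal is to provide estimates and preliminary data on these outcomes to inform the sample size needed for a larger trial".

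**The concern.** The background section describes LGA as birth weight above the 90th percentile. To classify a baby, the team must place its weight against a reference for gestational age. The plan then keeps only which side of the line the baby fell on. A change in size among babies who all stay above the line, or all below it, leaves no trace.

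At stake is what Aim 4 can hand to the next trial. Two LGA counts out of about ten give a very wide interval for the difference. They give no mean difference and no SD, so the sponsor could not use this pilot to plan a larger trial on a continuous fetal-size endpoint, or to judge whether such an endpoint would need fewer women.

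**Working it through.** **The plan's own figure.** The documents state no effect size, power or precision for Aim 4, so there is nothing to reproduce.

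**Inputs**
- 10 completers per group (Description of Population; Power and Sample Size). 12 per group is half of the up to 24 randomised.
- Alpha 0.05 for this aim, taken as two-sided.
- LGA rate 13/16 = 81.25%: 13 LGA infants among 16 women in the crossover study described under Background and Significance. 14 of those 16 continued closed-loop therapy until delivery, so this is not a SAPT rate.
- LGA rate 50%: my assumption, to show a range.
- Birth-weight z-score normal with equal SD in both arms: assumption.

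**Step 1. Information kept by the cut.** For a normal variable cut so that a share p is positive, with c the normal quantile of p, the information kept is φ(c)² / [p(1 − p)].
- p = 0.50: c = 0, φ = 0.3989; 0.1592 / 0.25 = 0.637.
- p = 0.8125: c = 0.887, φ = 0.2692; 0.0724 / 0.1523 = 0.476.

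Ten babies per arm scored yes/no carry about the information of 6.4 (at 50%) or 4.8 (at 81%) per arm measured on the full scale.

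**Step 2. Precision with 10 per arm.**
- LGA difference, same rate p in both arms: 1.96 × √[2p(1 − p)/10]. At 50% this is 0.438; at 80%, 0.351; at 81.25%, 0.342. The half-width is about 34 to 44 percentage points.
- Mean z-score difference, in SD units: t(0.975, 18 df) × √(2/10) = 2.101 × 0.447 = 0.94 SD.

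**Step 3. Power, for illustration only.** LGA rates p1 and p2 are converted to a shift d = z(p1) − z(p2). Power of the two-sample t-test on the z-score comes from the noncentral t. Power of the uncorrected chi-square comes from enumerating all binomial outcomes. Gaps are taken before rounding.

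| LGA rates | d (SD) | 10 per arm: t / chi-square / gap | 12 per arm: t / chi-square / gap |
|---|---|---|---|
| 81% vs 75% | 0.21 | 7.4 / 4.2 / 3.2 | 7.9 / 5.4 / 2.5 |
| 50% vs 40% | 0.25 | 8.4 / 6.2 / 2.1 | 9.1 / 9.5 / −0.3 |
| 81% vs 70% | 0.36 | 12.0 / 6.5 / 5.5 | 13.6 / 8.7 / 5.0 |
| 50% vs 30% | 0.52 | 19.9 / 12.8 / 7.1 | 23.3 / 19.0 / 4.3 |
| 81% vs 60% | 0.63 | 26.9 / 14.5 / 12.4 | 31.8 / 20.2 / 11.5 |
| 81% vs 50% | 0.89 | 46.7 / 27.6 / 19.2 | 54.7 / 38.3 / 16.4 |
| 81% vs 40% | 1.14 | 67.5 / 45.1 / 22.3 | 76.1 / 59.6 / 16.5 |

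Across these pairs the gap is about 2 to 6 points for shifts of 0.2 to 0.4 SD and 12 to 22 points for 0.6 to 1.1 SD at 10 per arm. At 12 per arm it runs from none to about 16 points. The starting rate matters: at 10 per arm, 0.6 SD from 50% gives 9 points and 1.0 SD from 50% gives 23.

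Departure from normality shrinks the gap. In simulation at 81% vs 50% with 10 per arm, power is 39% against 27% with heavy tails (t with 5 df) and 35% against 28% with a right-skewed shape.

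**The case against.** The strongest reply is that Aim 4 is exploratory, the plan disclaims power for it, and SA 4.2 hypothesises that rates are similar. Power to detect a difference is then the wrong yardstick. This stands. A reader might infer from Step 3 that the cut costs the trial a fixed number of points of power. The documents do not support that: they give no birth-weight effect, and the gap depends on the shift assumed, down to nothing in one case.

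A reader might also take 81% as the expected SAPT rate and suppose that closed-loop therapy would lower it. The 13 of 16 come from a crossover study in which most women used closed-loop therapy to delivery. The introduction itself says LGA rates remained high with that system.

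A third tempting step is to let the z-score answer SA 4.2 in place of LGA. The hypothesis is worded as rates of LGA and macrosomia, and the larger trial is to focus on these outcomes, so the rates are needed. A mean shift also cannot tell fewer large babies from more small ones, and the risk section names abnormal fetal size generally.

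It is fair, too, that the wide interval comes mainly from having 10 per arm. An interval of ±0.94 SD is itself weak: starting from a 50% LGA rate it spans about 17% to 83%. Finally, the plan names no reference standard and does not list infant sex among the delivery data.

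The reply does not remove the loss in Step 1. Being exploratory does not settle the matter when the stated purpose is to supply estimates for sizing a later trial. The plan already uses t-tests or Wilcoxon tests for continuous scores in Aims 2 and 3.

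**Conclusion.** The concern holds as a point about precision. Fetal size is analysed only as LGA yes/no although the continuous data are to be collected. Under a roughly normal z-score, the cut keeps about 64% of the information at an assumed 50% LGA rate and about 48% at 81%. LGA counts from 10 babies per arm leave a half-width of about 34 to 44 percentage points and supply no mean difference or SD.

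The size of the loss rests on normality and on LGA rates that are assumed or borrowed from a different cohort. No single power figure can be attached to it. The case is for adding a continuous estimate beside the rates, not for replacing them.

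**What to change.** In the Aim 4 paragraph of the Statistical Analysis Plan:

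1. Keep the LGA rates and add macrosomia. Report each by arm and as a difference with 95% confidence intervals, as the answer to SA 4.2 as worded.
2. Name the reference standard used to classify LGA.
3. Add a supplementary estimate of the HCL minus SAPT difference in birth weight adjusted for gestational age at delivery, or in birth-weight z-score from that same reference. Make it sex-specific only if infant sex is available in the delivery records. Report the 95% CI and the pooled SD.
4. State that this estimate will be used together with the LGA rates to plan the larger trial.

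The cost is a few sentences and one derived variable, with no extra visits or participants. The downside is one more exploratory estimate, itself imprecise, whose mean shift should be read beside the rates.
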